## 8.2. Adverse Events Analyses

Adverse events analyses including the analysis of adverse events (AEs), Serious (SAEs) and other significant AEs will be based on GSK Core Data Standards. The details of the planned displays are provided in [Appendix 9: List of Data Displays](#).

The eCRF texts for adverse events will be coded using the Medical Dictionary for Regulatory Activities (MedDRA), and will be reported using the primary System Organ Class (SOC) and the Preferred Term.

Adverse events will be summarized and grouped by primary SOC and by adverse event (i.e., Preferred Term) within primary SOC. Results will be displayed in the order of decreasing frequency, both across primary SOC and within primary SOC. The number of participants with one or more events of any type will also be calculated. The relationship of primary SOC, Preferred Terms, and verbatim text will be listed.

For each type of adverse events (e.g., AEs, drug-related AEs, serious AEs), where appropriate, three summary tables will be provided for the ITT population for the following treatment phases:

- On-treatment AEs
  - On-treatment AEs adjusted for exposure (per thousand person-years)
- Post-treatment AEs
- Post-study AEs.

For assignment of AEs to study phases see [Section 10.4.1](#).

Adverse events will also be summarized by gender, age, race and region as defined in [Section 5.5.2](#).

Adverse events during the run-in period will be summarized separately.

Adverse events for participants who received an incorrect treatment during the study will be listed.

## 8.3. Adverse Events of Special Interest Analyses

A comprehensive list of MedDRA terms based on clinical review will be used to identify each type of event. The details of the planned displays are provided in [Appendix 9: List of Data Displays](#).

Adverse events of special interest have been defined as AEs which have specified areas of interest for one or more of the treatment groups (UMEC 31.25mcg and UMEC 62.5mcg). These consist in groupings of preferred terms based on the MedDRA dictionary version used in each reporting effort. Subgroups may be defined, based on relevant combination of preferred terms, or on Standardized MedDRA queries (SMQ).

[Table 6](#) presents the special interest AE groups for FF and UMEC, defined upon the release of version 20.1 of the MedDRA dictionary.

**Table 6 AESI definitions**

Special Interest AE Group	Special Interest AE Subgroup	PTs for Inclusion
Cardiovascular effects*	Cardiac arrhythmia	Cardiac arrhythmia (SMQ), excluding congenital and neonatal arrhythmias
	Cardiac failure	Cardiac Failure (SMQ)
	Cardiac ischaemia	Myocardial Infarction (SMQ) Other Ischaemic Heart Disease (SMQ)
	Stroke	Central nervous system haemorrhages and cerebrovascular conditions (SMQ)
	Hypertension	Hypertension (SMQ)
Pneumonia*	Pneumonia	Infective Pneumonia (Narrow SMQ)
LRTI (excluding pneumonia SMQ)*	LRTI (excluding pneumonia SMQ)	Selected PTs
Decreased bone mineral density and associated fractures	Decreased bone mineral density and associated fractures	Osteoporosis/Osteopenia (SMQ) Selected PTs
Hypersensitivity*	Hypersensitivity	Hypersensitivity (SMQ) Angioedema (SMQ) Anaphylactic reaction (SMQ)
Anticholinergic Syndrome*	Anticholinergic syndrome	Anticholinergic Syndrome SMQ
Gastrointestinal obstruction*	Gastrointestinal obstruction	Gastrointestinal obstruction SMQ
Adrenal Suppression	Adrenal Suppression	Selected PTs
Antimuscarinic ocular effects / Corticosteroid Associated Eye Disorders	Glaucoma (antimuscarinic / corticosteroid)	Glaucoma (SMQ)
	Cataracts (corticosteroids)	Lens disorder (SMQ)
Effects on Glucose	Effects on Glucose	Hyperglycaemia/new onset diabetes mellitus (SMQ)
Local steroid effects	Local steroid effects	Selected PTs
Urinary retention*	Urinary retention	Selected PTs
Dry mouth / Drying airway secretions*	Dry mouth / Drying airway secretions	Selected PTs (narrow and broad focus)

\*: of interest for UMEC only.

Adverse events of special interest will be summarized in the same manner outlined in Section 8.2 for overall AEs.

#### **8.4. Major Adverse Cardiac Events (MACE)**

The MACE endpoint will be analyzed using broad and narrow definitions.

The Broad MACE will be defined as follows:

- Cardiac Ischaemia Special Interest AE Subgroup (Myocardial Infarction SMQ and Other Ischaemic Heart Disease SMQ) including fatalities,
- Stroke Special Interest AE Subgroup (Central Nervous System Haemorrhages and Cerebrovascular Conditions SMQ) including fatalities

The narrow MACE definition will include only the PTs of “myocardial infarction” and “acute myocardial infarction” in place of the Cardiac Ischaemia Special Interest AE subgroup.

#### **8.5. Clinical Laboratory Analyses**

Laboratory (hematology, clinical chemistry, and urinalysis) tests are performed at Screening (Visit 1) only. For hematology and clinical chemistry, laboratory values will be classified as ‘Low’, ‘Normal’, or ‘High’ based on the provided normal ranges. Only laboratory data for participants with at least one value outside the ‘Normal’ range will be listed.

#### **8.6. Other Safety Analyses**

The analyses of non-laboratory safety test results including ECGs and vital signs will be based on GSK Core Data Standards, unless otherwise specified. The details of the planned displays are presented in [Appendix 9: List of Data Displays](#).

##### **8.6.1. Vital Signs**

Vital signs (pulse rate, diastolic blood pressure, and systolic blood pressure) are measured at every clinic visit, starting at Visit 1, and prior to conducting spirometry.

For a given participant, the baseline value for each of the vital signs (pulse rate, diastolic blood pressure, and systolic blood pressure) is the last value recorded prior to randomized treatment start date, generally at Visit 2. Change from baseline value at post-randomization visits is the difference between the first recorded vital sign value at the clinic visit and the baseline value.

The ‘maximum/minimum post-baseline’ value will be derived as the maximum/minimum on-treatment value recorded at any scheduled, unscheduled, or Early Withdrawal (EW) visit after the start of study treatment.

See Section 8.6.4 for details on the statistical analysis of vital signs data.

### 8.6.2. ECG

12-lead ECGs are measured at Visit 1, and approximately 15-45 minutes after the administration of study treatment at Visits 3 and 5, and at Early Withdrawal visit. The ECG measurements of interest are QTc (F), heart rate, and PR interval. QTc(B) will also be summarized. All ECG data present in the database will be considered valid and will be reported (even if the ECG had a technical error).

For a given participant, the baseline value for each of the parameters is the last value recorded prior to randomized treatment start date, generally the assessment at Visit 1, but can be a repeat and/or unscheduled assessment. Change from baseline value at post-randomization visit is the difference between the first recorded ECG value at the clinic visit and the baseline value.

The ‘maximum/minimum post-baseline’ value will be derived as the maximum/minimum on-treatment value recorded at any scheduled, unscheduled, or Early Withdrawal (EW) visit after the start of study treatment. QTc (F) values (including ‘maximum post-baseline’) will be categorized as follows:  $\leq 450\text{msec}$ ,  $>450$  to  $\leq 480\text{msec}$ ,  $>480$  to  $\leq 500\text{msec}$ ,  $>500$  to  $\leq 530\text{msec}$  and  $>530\text{msec}$ . Change from baseline QTc (F) values (including change to ‘maximum post baseline’) will be categorized as follows:  $\leq -60\text{msec}$ ,  $>-60$  to  $\leq -30\text{msec}$ ,  $>-30$  to  $\leq 0\text{msec}$ ,  $>0$  to  $\leq 30\text{msec}$ ,  $>30$  to  $\leq 60\text{msec}$ , and  $>60\text{msec}$ .

See Section 8.6.4 for details on the statistical analysis of QTc (F) and PR interval data.

An ‘any time post-baseline’ ECG interpretation will be derived as the worst on-treatment interpretation recorded at a scheduled, unscheduled, or EW visit after the start of study treatment. The worst case post-baseline is defined as:

- ‘Abnormal’ if any on-treatment assessment is evaluated as ‘Abnormal’
- ‘Unable to evaluate’ if all on-treatment assessments are ‘Unable to evaluate’
- ‘Normal’ if any on-treatment assessment is evaluated as ‘Normal’ and there are no on-treatment assessments evaluated as ‘Abnormal’

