#### 8.6.4. Planned Statistical Analyses of Safety Endpoints

Statistical Analysis of Safety Endpoints	
Endpoints	

• Change from baseline in Systolic BP

• Change from baseline in Diastolic BP

• Change from baseline in Pulse rate

• Change from baseline in PR interval;

• Change from baseline in QTc (F) interval

	
Model Specification, Checking, Results Presentation and SAS code	

• These endpoints will be analyzed using the same methodology as for the primary analysis of trough FEV1 as outlined in Section 7.1.

• All on-treatment data collected at scheduled clinic visits will be included.

	

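### ECGs with a technical error count as valid, so faulty values can enter the QTcF and PR change analyses and set the QTcF maximum and category

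*SAP*

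**What the plan says.** Section 8.6.2 sets the validity rule for ECG data: "All ECG data present in the database will be considered valid and will be reported (even if the ECG had a technical error".

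The derivations in the same section then use the data as follows.

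- **Visit change.** Change from baseline at a post-randomization visit "is the difference between the first recorded ECG value at the clinic visit and the baseline value".
- **Baseline.** This is "the last value recorded prior to randomized treatment start date, generally the assessment at Visit 1, but can be a repeat and/or unscheduled assessment".
- **Maximum and minimum post-baseline.** These are the "maximum/minimum on-treatment value recorded at any scheduled, unscheduled, or Early Withdrawal (EW) visit after the start of study treatment".
- **Categories.** QTcF values and QTcF changes, each including the maximum post-baseline, are put into bands. The top bands are above 530 msec for the value and above 60 msec for the change.

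Section 8.6.4 models change in PR and QTcF by the primary-endpoint method and states: "All on-treatment data collected at scheduled clinic visits will be included". The SAP nowhere excludes a technical-error tracing, replaces it with a repeat, or plans an analysis without it. Where several values fall in one window, Section 10.3 gives priority to the scheduled visit and does not consider quality.

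**The concern.** The wording goes beyond a promise to list faulty tracings. Calling them valid admits them to every derivation that follows. Two separate routes matter.

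The first is the visit value. If the first tracing at Week 4 or Week 24 was technically faulty but produced intervals, that value enters the change summaries and models, and a later valid repeat does not displace it.

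The second is the maximum. It does not depend on the first-value rule. It takes the extreme of everything recorded on treatment, so a spuriously long faulty QTcF can become the maximum whether or not a repeat was done.

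QTcF and PR are the only ECG parameters that are modelled, and the high QTcF bands are among the first things a safety reader looks at. Noise in the models can blur a real shift, and a false entry in a top band has to be explained case by case. The category and maximum displays are for QTcF only; PR is affected through its summaries and model.

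**Working it through.** The SAP states no figure on this point, so there is none to reproduce. The check compares the SAP's own rules and then gives a sense of scale.

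**Rules side by side**

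| Data | Rule for a poor or repeated measurement | Where |
|---|---|---|
| ECG, post-randomization change | first recorded value; technical errors count as valid | 8.6.2 |
| ECG, baseline | last recorded value, which may be a repeat | 8.6.2 |
| ECG, maximum/minimum | extreme of all on-treatment values | 8.6.2 |
| ECG, overall interpretation | an unevaluable reading counts only if every on-treatment reading is unevaluable | 8.6.2 |
| Clinic FEV1, baseline | must be acceptable or borderline acceptable | 5.2.1 |
| Spirometry, unacceptable | set to missing and left out of listings and summaries | 10.7.2 |

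A repeat can thus replace a faulty tracing before treatment but not in the visit change afterwards. The numeric ECG intervals are the only entries here with neither a quality condition nor an override.

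**Scale from the SAP's own counts**

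- Randomized (Section 5.4): 174 + 69 + 21 + 114 + 58 = 436, and 436 / 3 ≈ 145 per arm.
- One false outlier: 1 / 145 ≈ 0.7 percentage points of an arm.
- A 60 msec error in one participant: 60 / 145 ≈ 0.4 msec on the unadjusted arm mean at that visit.

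**Scale under assumptions (none of these values is in the SAP)**

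With two scheduled on-treatment ECGs and an error probability e per tracing, the chance of at least one faulty tracing is 1 − (1 − e)². This is 2.0%, 4.0% and 9.8% for e = 1%, 2% and 5%. It is the chance of having any faulty tracing, not of a false maximum or outlier.

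Noise in the models: let the true change have SD s, and let a faulty tracing add an error of mean 0 and SD a. The per-visit SD becomes √(s² + e·a²).

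- s = 15, e = 1%, a = 40: √(225 + 16) = 15.5, ratio 1.03
- s = 15, e = 5%, a = 60: √(225 + 180) = 20.1, ratio 1.34
- s = 20, e = 1%, a = 40: √(400 + 16) = 20.4, ratio 1.02
- s = 20, e = 5%, a = 60: √(400 + 180) = 24.1, ratio 1.20

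The unadjusted standard error of a visit difference would thus be about 2% to 34% larger across these settings.

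Outliers: a simulation of 400,000 participants used the same values of s and a, with e = 1%, 2% or 5%, mean true change 0 and within-participant correlation 0.5. Every faulty tracing was given both a numeric QTcF and a valid repeat. Results were scaled to the planned 128 per arm (Section 2.3). The expected number with a maximum change above 60 msec was 0.2 to 2.6 under the SAP rule. With faulty tracings set aside it was about 0.01 (s = 15) or 0.3 (s = 20).

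**The case against.** The strongest defence is that keeping every value is explicit, fixed in advance and the same in all blinded arms. It cannot favour a treatment, and it is conservative for counting QTc outliers because no prolonged value can be removed by a quality flag. That stands, and it is why the all-tracings outlier displays should be kept. It does not carry over to the models, where added noise is not conservative: it can mask a real shift.

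A second objection is that the SAP does not say whether a technical-error tracing carries intervals at all. If it does not, the first recorded value at the visit is already the repeat's. That also stands, so faulty values can enter the analyses; the text does not show that they will.

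Third, the last-before, first-after convention is not peculiar to faulty ECGs, since Section 8.6.1 uses it for vital signs. Nor is baseline fully protected: the last pre-treatment value may itself be faulty. Both are correct, and the baseline rule needs the same repair.

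Fourth, ECG endpoints lie outside the testing hierarchy in Section 5.6, so no formal efficacy conclusion depends on them. This limits the stakes.

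A reader might infer that 2% to 10% of participants would have a false maximum. The documents do not support that. The error rates behind those percentages are assumed, and a faulty tracing changes a category only if its error is upward, it is the participant's highest value and it crosses a band limit. A reader might also infer bias between arms; a rule applied identically under blinding gives no ground for that.

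**Conclusion.** The point holds in limited form. Section 8.6.2 admits measurements known to be faulty to the numeric ECG analyses. Where such a tracing carries intervals, it can supply the visit value for the QTcF and PR change summaries and models despite a valid repeat. By a separate route, it can set a participant's maximum QTcF and category. The harm is noise and possible false outliers, without direction between arms.

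The size cannot be taken from the SAP. The per-participant figures (about 0.7 percentage points and 0.4 msec) need only the arm size and, for the second, a supposed 60 msec error. The standard-error and outlier ranges rest wholly on assumed error rates, error sizes and SDs, and show only that the effect could run from negligible to noticeable. The change is worth making because it is cheap and brings ECG handling closer to the SAP's own practice for spirometry.

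**What to change.** Replace the validity sentence in Section 8.6.2 with the following rules, and align Section 8.6.4.

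1. Flag technical-error tracings before unblinding and list all of them.
2. For the QTcF and PR change-from-baseline summaries and models, use the valid repeat at that visit where one exists; otherwise set the visit value to missing.
3. Apply the same rule when choosing the baseline value.
4. Present the maximum post-baseline and QTcF category displays twice, once with all tracings and once without the flagged ones, so that no prolonged value is hidden.

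The cost is SAP wording, a data filter and a few added displays. A few visit values become missing. Fixing the flags before unblinding guards against selective exclusion.

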### 8.6.3. Pregnancy

Any pregnancies reported during the study will be summarized in case narratives. Any pregnancy complication or elective termination of a pregnancy for medical reasons will be recorded as an AE or SAE and included in summaries and listings of AEs/SAEs.

#### 8.6.4. Planned Statistical Analyses of Safety Endpoints

Statistical Analysis of Safety Endpoints	
Endpoints	

• Change from baseline in Systolic BP

• Change from baseline in Diastolic BP

• Change from baseline in Pulse rate

• Change from baseline in PR interval;

• Change from baseline in QTc (F) interval

	
Model Specification, Checking, Results Presentation and SAS code	

• These endpoints will be analyzed using the same methodology as for the primary analysis of trough FEV1 as outlined in Section 7.1.

• All on-treatment data collected at scheduled clinic visits will be included.

	

## 10. APPENDICES

### 10.1. Appendix 1: Protocol Deviation Management

Protocol deviations (PDs) will be tracked by the study team throughout the conduct of the study in accordance with the Protocol Deviation Management Plan.

- Data will be reviewed prior to unblinding and freezing the database to ensure all important deviations are captured and categorised on the protocol deviations dataset.
- Participants who received an incorrect container will be captured as an important protocol deviation. The actual treatment in the incorrect container will be identified by S&P and, if applicable, recorded as incorrect treatment per randomization schedule and quality controlled prior to SDTM DBF.
- This dataset will be the basis for the summaries and listings of protocol deviations.

Important protocol deviations (including deviations related to study inclusion/exclusion criteria, conduct of the trial, participant management or participant assessment) will be summarized and listed.

A separate summary and listing of all inclusion/exclusion criteria deviations will also be provided. This summary will be based on data as recorded on the inclusion/exclusion page of the eCRF.

No per-protocol analysis is planned for this study.

## 10.2. Appendix 2: Schedule of Activities

### 10.2.1. Protocol Defined Schedule of Events

Protocol Activity	Pre-Screen	Screen Run-in	Treatment Period				Follow-up	
			2 Randomization	3	4	5/End of Study (EOS)	Early Withdrawal (EW)	Safety Follow-up Contact
Visit	0	1						
Study Day	-42 to -14	-14	1	29	85	169		
Week	-6 to -2	-2	0	4	12	24		1 week after Visit 5/EOS or EW Visit
Window				-5/+2d	-5/+2d	-5/+2d		-1/+4d
Informed consent (ICF) a	X							
Genetic ICF b	X							
Inclusion and exclusion criteria		X	X					
Demography c	X	X						
Medical history		X						
Asthma history d		X						
Exacerbation history		X						
Smoking History and status		X						
Concomitant medication review	X	X	X	X	X	X	X	X

Protocol Activity	Pre-Screen	Screen Run-in	Treatment Period				Follow-up	
			2 Randomization	3	4	5/End of Study (EOS)	Early Withdrawal (EW)	Safety Follow-up Contact
Visit	0	1						
Study Day	-42 to -14	-14	1	29	85	169		
Week	-6 to -2	-2	0	4	12	24		1 week after Visit 5/EOS or EW Visit
Window				-5/+2d	-5/+2d	-5/+2d		-1/+4d
Register visit in Interactive Web Response System (IWRs) (RAMOS NG) e	X	X	X	X	X	X	X	
Randomization f			X					
Laboratory Assessments								
Urinalysis		X						
Hematology and clinical chemistry g		X						
Hepatitis B and C		X m						
Genetic sample			X n					1.
Serum pregnancy test		X o				X o	X o	
Urine pregnancy test			X o	X o	X o			
Safety Assessments								
Physical exam including height and weight h		X				X	X	
12-lead Electrocardiogram (ECG) i		X		X		X	X	
Vital signs j		X	X	X	X	X	X	
Adverse Event (AE) review		X	X	X	X	X	X	X

Protocol Activity	Pre-Screen	Screen Run-in	Treatment Period				Follow-up	
Visit	0	1	2 Randomization	3	4	5/End of Study (EOS)	Early Withdrawal (EW)	Safety Follow-up Contact
Study Day	-42 to -14	-14	1	29	85	169		
Week	-6 to -2	-2	0	4	12	24		1 week after Visit 5/EOS or EW Visit
Window				-5/+2d	-5/+2d	-5/+2d		-1/+4d
Serious Adverse Event (SAE) review	X	X	X	X	X	X	X	X
Study Treatment								
Dispense Albuterol/Salbutamol I, as required		X	X	X	X			
Collect Albuterol/Salbutamol I, as required			X	X	X	X	X	
Dispense open label fluticasone furoate (FF) 100 mcg medication		X	X	X	X			
Administer open label FF 100 mcg		X	X	X	X	X		
Collect open label FF 100 mcg			X	X	X	X	X	
Dispense double-blind study treatment			X	X	X			
Administer double-blind study treatment			X p	X p	X p	X p		
Collect double-blind study treatment				X	X	X	X	
Assess FF 100 mcg run-in medication compliance			X					

Protocol Activity	Pre-Screen	Screen Run-in	Treatment Period				Follow-up	
Visit	0	1	2 Randomization	3	4	5/End of Study (EOS)	Early Withdrawal (EW)	Safety Follow-up Contact
Study Day	-42 to -14	-14	1	29	85	169		
Week	-6 to -2	-2	0	4	12	24		1 week after Visit 5/EOS or EW Visit
Window				-5/+2d	-5/+2d	-5/+2d		-1/+4d
Assess FF 100 mcg and double-blind study treatment compliance				X	X	X	X	
Efficacy Assessments								
Global Assessment of Severity k			X	X	X	X	X	
Global Assessment of Response to Treatment k				X	X	X	X	
Asthma Control Questionnaire (ACQ-6) k		X	X q					
Asthma Control Questionnaire (ACQ-5) k				X	X	X	X	
St. George's Respiratory Questionnaire (SGRQ) k			X	X	X	X	X	
Asthma Quality of Life Questionnaire (AQLQ) k			X	X	X	X	X	

Protocol Activity	Pre-Screen	Screen Run-in	Treatment Period				Follow-up	
Visit	0	1	2 Randomization	3	4	5/End of Study (EOS)	Early Withdrawal (EW)	Safety Follow-up Contact
Study Day	-42 to -14	-14	1	29	85	169		
Week	-6 to -2	-2	0	4	12	24		1 week after Visit 5/EOS or EW Visit
Window				-5/+2d	-5/+2d	-5/+2d		-1/+4d
Evaluating Respiratory Symptoms (E-RS) +Asthma symptoms + Peak Expiratory Flow (PEF) + Home Forced Expiratory Volume in 1 second (FEV1 k,l )						X		
eDiary Dispense		X						
eDiary Collect						X	X	
eDiary Review			X	X	X	X	X	
Dispense paper Medical Problems/Medications Taken worksheet	X	X	X	X	X			
Review paper Medical Problems/Medications Taken worksheet		X r	X	X	X	X	X	
Reversibility			X	X	X	X	X	
Exacerbation assessment			X	X	X	X	X	
Pre-dose spirometry (clinic)		X s	X s	X s	X s	X s	X s	
Post-dose spirometry (clinic)			X t			X t	X t	

- a) The ICF must be signed before any study procedures, including medication cessation.
- b) Genetics research consent may be obtained at the same time as the study IC and must be obtained prior to obtaining a genetic blood sample.
- c) Demography may be captured at either the Pre-screen Visit or Screening Visit (for participants who do not have a Pre-screen Visit).
- d) The assessment of asthma history will include: the age of the participant when they were first provided with an inhaler for asthma; completion of an asthma medical history questionnaire (a copy of this questionnaire and instructions for its use can be found in the SRM).
- e) The IWRS will be used for randomization, emergency unblinding and study treatment supply management (Please refer to the RAMOS NG IWRS manual and SRM for more information).
- f) Participants must not be randomized prior to confirming their eligibility to participate in the study.
- g) If test otherwise performed within 3 months prior to first dose of study treatment, testing at screening is not required.
- h) Physical Examination will include height and weight at Visit 1 only.
- i) At the Screening Visit (Visit 1), the ECG is to be obtained after the vital signs assessment but prior to performing the pre-bronchodilator spirometry assessment (see Section 9.4.3 of the protocol). At all post randomization visits the ECG is to be obtained 15 minutes to 45 minutes after the administration of study treatment.
- j) The vital signs assessment will include the measurement of blood pressure, heart rate.
- k) Assessment(s) to be completed prior to the administration of study treatment.
- l) To be completed using the provided combined spirometer/eDiary device. Assessments should be completed in the morning upon wakening and in the evening immediately prior to going to bed.
- m) Hepatitis C RNA is optional however a confirmatory negative Hepatitis C RNA test must be obtained, to be able to enrol participants with positive Hepatitis C antibody due to prior resolved disease. Hep B/C: If test otherwise performed within 3 months prior to first dose of study treatment, testing at screening is not required.
- n) Pharmacogenetic sample may be drawn any time from Visit 2 onwards.
- o) Assessments only to be conducted in females of reproductive potential.
- p) Study treatment should be administered at approximately the same time of day at each applicable clinic visit.
- q) Baseline ACQ-5 will be derived from items 1-5 of the Randomization (Visit 2) ACQ-6.
- r) Following completion of the pre-dose spirometry assessments, the reversibility test will be conducted between 20 and 60 minutes following 4 inhalations of albuterol/salbutamol or ipratropium aerosol. If airway reversibility is not demonstrated at Visit 1 then the assessment may be repeated within 7 days of Visit 1 (see Section 9.4.3 of the protocol. for details of the criteria to be met before a repeat of the reversibility assessment is permitted). If airway reversibility is successfully demonstrated at the second attempt and all other eligibility criteria assessed at Visit 1 are met then the participant may enter the 2-week run-in period.
- s) Pre-dose spirometry should be performed between 6am and 11am after withholding rescue medication for at least 6 hours and prior to taking the morning dose of study treatment and FF 100 mcg. After V2 pre-dose spirometry assessments should be performed within  $\pm$  1 hour of the V2 spirometry.
- t) Post-dose spirometry is to be performed 3 hours ( $\pm$  15 minutes) after taking the morning dose of study treatment. Rescue medication should be withheld for at least 6 hours prior to the pre-dose spirometry assessments until after completion of the 3-hour post-dose spirometry assessments. Pre- and post-dose spirometry assessments should be performed within  $\pm$  1 hour of the V2 spirometry.

